### **Analyses in individual years**

There will be approximately 4,100 child-years of observation in the year following the third booster; 1367 child-years in each study group. Assuming the incidence of clinical episodes of malaria remains at about 200 episodes per 1,000 children per year during this period, the study will have 90% power, through a standard superiority comparison, to detect a 25.9% or greater

relative difference (absolute difference: 52 cases per 1000 child-years) between the Combined RTS,S/AS01E + SMC group and the RTS,S/AS01E alone or SMC alone group.

A similar analysis will be undertaken for the final year of the study following administration of a fourth booster dose of the RTS,S/AS01E or comparator vaccine but study power will be reduced because slightly more than half of the children enrolled (3860/5920) will not be eligible for SMC in 2021-22, and thus will not contribute further events nor person-time at risk to the study period.

## Study outcomes

### Primary Endpoint

The primary end-point is the incidence of episodes of clinical malaria, as defined below, treated at a study health centre or hospital.

1.1 **Clinical malaria** is defined as an episode of fever (either measured axillary temperature  $\geq 37.5^{\circ}\text{C}$ , or a history of fever within the past 48 hours), and a positive blood film, with a *Plasmodium falciparum* parasite density of 5,000 per  $\mu\text{l}$  or more. This cut-off was used in the original three-year trial, as well as in previous studies of SMC in Burkina Faso and Mali, and in the phase 3 studies of the RTS,S/AS01 vaccine (1, 2, 5-7).

All passively-detected episodes of clinical malaria will be included in the analysis. Specifically, this includes visits to outpatient clinics and hospitals, as well as morbidity detected at the time of SMC or at the end of transmission season survey. These contacts can be considered 'passive' because the caregiver had to bring the child to the contact and because the SMC or survey was conducted at the health facility in many cases. As the focus is on passively detected cases, morbidity detected during home visits for serological sampling, and for the weekly parasitaemia survey (which was undertaken only in the initial phase of the study) are excluded. Morbidity detected at the time of vaccination is also excluded, because some children were visited at home and brought to the clinic in order to be vaccinated, so cases found at the time of vaccination cannot be regarded as passively detected.

To avoid double counting of disease episodes which result in more than one healthcare contact, episodes of the primary outcome documented within 7 days of a previous episode will not be counted. No adjustment is necessary to the person-time at risk (11).

### Secondary Endpoints

Secondary end-points - not listed in order of priority - include the following:

#### 2.1 Morbidity events detected passively at study health centres and hospitals

As for the primary outcome, episodes of the outcomes listed below which occur within 7 days of a previous event of the same type will be discounted. No adjustment is necessary to the person-time at risk (11).

2.1.1 **Clinical malaria with *P. falciparum* parasitaemia of any density.** Defined as an episode of fever (either measured temperature  $\geq 37.5^{\circ}\text{C}$ , or a history of fever within the past 48 hours), and a positive blood film for *P. falciparum* parasites. This includes hospitalisations for malaria meeting the above criteria (i.e. fever or history of fever, plus slide confirmed *P. falciparum* malaria of any density).

2.1.2 **Clinical malaria confirmed by rapid diagnostic test.** Defined as an episode of fever (either measured temperature  $\geq 37.5^{\circ}\text{C}$ , or a history of fever within the past 48 hours), and a positive rapid diagnostic test (RDT).

2.1.3 **Clinical malaria with non-falciparum parasitaemia of any density.** Defined as an episode of fever (either measured temperature  $\geq 37.5^{\circ}\text{C}$ , or a history of fever within the past 48 hours), and a positive blood film for non-falciparum *Plasmodium* parasites.

2.1.4 **Clinical malaria with *Plasmodium spp.* infection of any density.** Defined as an episode of fever (either measured temperature  $\geq 37.5^{\circ}\text{C}$ , or a history of fever within the past 48 hours), and a positive blood film for any *Plasmodium spp.* parasites (i.e. including *P. falciparum*).

## 2.2 Severe outcomes detected passively at study health centres and hospitals, and through verbal autopsies

For all hospital admissions and deaths, the primary diagnosis by a study physician was reviewed by a second independent clinician. A third clinician reviewed cases of disagreement to reach a consensus primary diagnosis. All verbal autopsies were also reviewed by the same process to obtain a consensus cause of death.

### 2.2.1 Hospital admissions due to any cause

### 2.2.2 Hospital admissions excluding those due to external causes or surgical conditions

2.2.3 **Hospital admissions due to malaria.** Defined as hospital admissions where malaria was the primary diagnosis, supported by a positive blood smear. Children who were admitted with a diagnosis of severe anaemia or neurological signs, with documented antimalarial treatment in the past 4 weeks, were also deemed to be due to malaria if their malaria RDT was positive (even if the blood smear result was negative or the blood smear result was not available). Additional analyses of children who meet the WHO criteria for a diagnosis of severe malaria including those with a) cerebral malaria, b) severe anaemia and c) other forms of severe malaria will be undertaken.

### 2.2.4 The incidence of blood transfusions in study hospitals

### 2.2.4 Deaths due to any cause

### 2.2.6 Deaths due to any cause excluding external causes and surgical conditions

2.2.7 **Deaths due to malaria.** Defined as hospital admissions resulting in death, where malaria was recorded as the primary cause of death supported by a positive blood smear. Children who were admitted with a diagnosis of severe anaemia or neurological signs, with documented antimalarial treatment in the past 4 weeks, were also deemed to be due to malaria

if their malaria RDT was positive (even if the blood smear result was negative or the blood smear result was not available). Deaths in the community will also be included when malaria is assigned by a panel of three independent physicians as the primary cause of death from verbal autopsy .

### **2.3 Outcomes measured at cross-sectional surveys at the end of the malaria transmission season**

For each of the outcomes below, results will be analysed and presented separately for the two surveys conducted during the extension study (conducted in November/December 2020 and November/December 2021).

- 2.3.1 The prevalence of asexual stage *P. falciparum* infection of any density
- 2.3.2 The prevalence of asexual stage *P. falciparum* infection with density  $\geq 5000$  per  $\mu\text{l}$
- 2.3.3 The prevalence of sexual stage *P. falciparum* infection (i.e. gametocytes)
- 2.3.4 The arithmetic mean *P. falciparum* parasite density, including samples which are parasite negatives as having a density of zero.
- 2.3.5 The prevalence of asexual stage infection of non-falciparum *Plasmodium* species.
- 2.3.6 The prevalence of sexual stage infection (i.e. gametocytes) of non-falciparum *Plasmodium* species.
- 2.3.7 The mean haemoglobin concentration in g/dL.
- 2.3.8 The prevalence of anaemia, defined as measured Hb  $< 10$  g/dL.
- 2.3.9 The prevalence of moderate anaemia, defined as measured Hb  $< 7$  g/dL.
- 2.3.10 The prevalence of severe anaemia, defined as measured Hb  $< 5$  g/dL.

### **2.4 The antibody response to sixth and seventh doses of the RTS,S/AS01E vaccine**

- 2.4.1 The *Plasmodium falciparum* anti-CSP antibody titre before and after the sixth and seventh doses (third and fourth 'booster' doses) of the RTS,S/AS01E malaria vaccine.
- 2.4.2 The association between the magnitude of the anti-CSP antibody response to the sixth and seventh doses of the RTS,S/AS01E vaccine and the risk of malaria during the subsequent malaria transmission season.

### **2.5 The treatment efficacy of the SP+AQ combination used for SMC**

- 2.5.1 The percentage of children with asymptomatic *P. falciparum* parasitaemia at the cross-sectional survey in November/December 2021, who, when treated with SP+AQ, have an adequate clinical and parasitological response (ACPR) after 28 days.

### **Serious Adverse Events**

In addition to the comparison of incidence rates described above, serious adverse events (SAEs) defined as hospitalisations or death, occurring at any time during the study will be tabulated by study group according to their cause.

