##### A.2 Definition of Adverse Events of Special Interest

AEs of specific interest for safety monitoring include all seizures occurring within 30 days post-vaccination, meningitis and pIMDs and will be recorded in the CRF.

Meningitis cases: For the further evaluation of the safety signal of meningitis in the investigational vaccine groups all cases of meningitis occurring during the study will be reported as a SAE.

pIMDs are a subset of AEs that include autoimmune diseases and other inflammatory and/or neurologic disorders of interest which may or may not have an autoimmune etiology. AEs that need to be recorded and reported as pIMDs include those listed in Table A.

Table A. List of Potential Immune-mediated Diseases:

| Neuroinflammatory disorders  | Musculoskeletal disorders  | Skin disorders  |
|--|--|---|
| 
 
• Cranial nerve disorders, including paralyses/paresis (e.g. Bell's palsy)
 
• Optic neuritis
 
• Multiple sclerosis
 
• Transverse myelitis
 
• Guillain-Barré syndrome, including Miller Fisher syndrome and other variants
 
• Acute disseminated encephalomyelitis, including site specific variants: e.g. non-infectious encephalitis, encephalomyelitis, myelitis, myeloradiculoneuritis
 
• Myasthenia gravis, including Lambert-Eaton myasthenic syndrome
 
• Immune-mediated peripheral neuropathies and plexopathies,
 
 | 
 
• Systemic lupus erythematosus and associated conditions
 
• Systemic scleroderma (Systemic sclerosis), including diffuse systemic form and CREST syndrome
 
• Idiopathic inflammatory myopathies, including dermatomyositis
 
• Polymyositis
 
• Antisynthetase syndrome
 
• Rheumatoid arthritis, and associated conditions including juvenile chronic arthritis and Still's disease
 
• Polymyalgia rheumatica
 
• Spondyloarthritis, including ankylosing spondylitis, reactive arthritis (Reiter's
 
 | 
 
• Psoriasis
 
• Vitiligo
 
• Erythema nodosum
 
• Autoimmune bullous skin diseases (including pemphigus, pemphigoid and dermatitis herpetiformis)
 
• Alopecia areata
 
• Lichen planus
 
• Sweet's syndrome
 
• Localised Scleroderma (Morphea)
 
 |

|  |  |  |
|--|--|--|

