| 
Liver disorders
 
 
• Autoimmune hepatitis
 
• Primary biliary cirrhosis
 
• Primary sclerosing cholangitis
 
• Autoimmune cholangitis
 
  | 
Gastrointestinal disorders
 
 
• Inflammatory Bowel disease, including Crohn's disease, ulcerative colitis, microscopic colitis, ulcerative proctitis
 
• Celiac disease
 
• Autoimmune pancreatitis
 
   | 
Endocrine disorders
 
 
• Autoimmune thyroiditis (including Hashimoto thyroiditis)
 
• Grave's or Basedow's disease
 
• Diabetes mellitus type I
 
• Addison's disease
 
• Polyglandular autoimmune syndrome
 
• Autoimmune hypophysitis
 
  |

A serious adverse event is any clinical condition that fulfils at least one of the following criteria:

- (1) Results in death.
- (2) Results in admission to hospital.
- (3) Is life-threatening (the child was at risk of death at the time of the adverse event).
- (4) Results in disability/incapacity.

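### The SAP's definition of a serious adverse event is narrower than the protocol's, so its SAE table by study group could omit protocol-defined SAEs

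*Combined protocol and SAP*

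**What the plan says.** **Protocol.** Appendix 2, section A, sets a rule under which one criterion is enough: "A serious adverse event is any clinical condition that fulfils at least one of the following criteria". Four criteria follow. They are death, admission ("Results in admission to hospital"), a life-threatening event, and disability ("Results in disability/incapacity"). Section A.2 of the same appendix adds a rule for one condition: "all cases of meningitis occurring during the study will be reported as a SAE". Section 4.2.2(e) makes the incidence of SAEs throughout the study part of the secondary safety endpoint, and singles out meningitis and cerebral malaria. Section 10.1 says that the SAP will set out how the secondary endpoints are measured.

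**SAP.** The section Serious Adverse Events plans one tabulation: "serious adverse events (SAEs) defined as hospitalisations or death, occurring at any time during the study will be tabulated", by study group and according to cause. It mentions neither life-threatening nor disabling events and does not refer to Appendix 2.

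Under Safety signals from the RTS,S/AS01 phase 3 studies, the SAP also plans separate analyses of meningitis, cerebral malaria, febrile convulsions and mortality by sex. The meningitis analysis is an incidence rate with a 95% confidence interval in RTS,S recipients over the intervention period. The SAP notes that there were no meningitis events in the first three years.

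**The concern.** The same term has two meanings in the two documents, and the narrower one governs the table that compares the study groups. The SAP does not flag or justify the change, although it alters how a protocol secondary endpoint is counted.

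The stake is completeness for rare events. Protocol section 8.1 says that sixth and seventh doses of RTS,S/AS01 have not been given before. For a rare serious outcome, the reader of the final report needs every protocol-defined case, by group. If one is missing from the SAP table but present in the listings sent to the DSMB and the manufacturer under section 8.1 and Appendix 2, section D, the two accounts of trial safety disagree and nothing in the plan explains why.

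**Working it through.** No sample size, power or error rate is involved, and the plan gives no figure to reproduce. The check sets the two definitions side by side.

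| Event | SAE under protocol Appendix 2 | In the SAP's SAE table |
|---|---|---|
| Death | Yes | Yes |
| Hospital admission | Yes | Yes |
| Life-threatening, not admitted, survived | Yes | No |
| Disability or incapacity, not admitted, survived | Yes | No |
| Meningitis, not admitted, survived | Yes | No |

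**Step 1: relation between the sets.** Every event in the SAP set is in the protocol set. Three kinds of event are in the protocol set only. The SAP set is therefore a strict subset.

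**Step 2: size of the shortfall.** Let N be the number of protocol-defined SAEs and n the number among them that were neither admitted nor fatal. The SAP table holds N − n events, a share of 1 − q with q = n/N. The documents give neither N nor n. If every life-threatening, disabling or meningitis event led to admission or death, n = 0 and nothing is lost. Otherwise the table is short by n. For meningitis in the first three years the loss is zero, because the SAP reports no events.

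**Step 3: whether another SAP analysis recovers the omitted events.**
- The severe outcomes in SAP section 2.2 are hospital admissions, transfusions in study hospitals and deaths. An event treated outside hospital and survived is in none of them.
- The meningitis rate is not tied to admission, so it would pick up a non-admitted case in an RTS,S recipient. It gives no count for the SMC alone group and no comparison by group.
- Cerebral malaria and febrile convulsions have their own comparisons with the SMC alone group.
- No SAP analysis would recover a disabling event, or a life-threatening event of another kind, without admission or death.

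**Step 4: whether such events could reach the database.** Protocol section 8.1 keeps SAE surveillance running throughout the study, and section 7.6.1 places project staff in dispensaries as well as in the district hospital. Appendix 2, section D, requires a report form for every SAE. A non-admitted SAE can therefore be recorded, although the main route described in section 8.1 is through admitted children.

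**The case against.** The strongest reply is that the difference may have no effect. Section 8.1 describes hospital staff identifying admitted children, and meningitis is worked up from cerebrospinal fluid, which points to hospital care. Appendix 1 describes serious events as mainly deaths or admissions. A child with a life-threatening illness who is seen at all will usually be admitted. This stands. A reader might infer that the SAP table will under-count SAEs, but no passage reports or predicts an SAE that was neither admitted nor fatal. The documents support "could" and not "will".

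Three further inferences are tempting and also go too far.

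- *That the SAP ignores meningitis.* It does not. The separate rate has no admission requirement. What is missing is a count for each of the three groups.
- *That safety oversight is impaired.* Section 8.1 and Appendix 2, section D, send all SAEs to the DSMB and the manufacturer without limiting them to admissions and deaths. The defect is confined to the SAP's SAE table.
- *That the loss can be expressed as a shift in an upper confidence limit when one event replaces zero.* The SAP plans no such limit for the SAE table. The rare event for which it plans a single-rate interval is meningitis, and the SAE definition does not govern that interval. No numerical size is supported.

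Potential immune-mediated diseases do not extend the point either. Appendix 2 treats them as a subset of adverse events and, unlike meningitis, does not make each one an SAE. Only those that meet a seriousness criterion are affected.

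None of this removes the mismatch. If the two definitions give the same counts in practice, using the protocol's wording loses nothing.

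**Conclusion.** The concern holds as an inconsistency between the protocol and the SAP. The SAP defines the SAEs to be tabulated by group as a strict subset of those defined in Appendix 2, without explanation. Its SAE table could omit life-threatening, disabling or meningitis events that were neither admitted nor fatal, and could then disagree with the listings sent to the DSMB and the manufacturer.

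The mismatch itself is certain, because it rests only on the two texts. Its numerical effect is unknown and may be zero, because it depends on a count that the documents do not give. For meningitis the residue is narrower: a rate is planned, but only in RTS,S recipients and without a comparison by group. The correction is small and should be made, because the affected table reports a protocol secondary endpoint and the repair is nearly free.

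**What to change.** In the SAP section Serious Adverse Events, replace the two-part definition with a reference to protocol Appendix 2: the four criteria plus all meningitis cases. Tabulate SAEs by study group and cause, with hospitalisation and death kept as sub-rows so that the planned figures remain visible. Add meningitis counts for all three groups beside the planned rate in RTS,S recipients.

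The change should be made before the treatment codes are released.

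The cost is a short change of text and a little extra tabulation. SAE reports are already required for every protocol-defined SAE. One practical point needs attention: the form content listed in Appendix 2, section D, does not name the seriousness criterion. It may have to be derived from the severity grade (which has a life-threatening level), the outcome code (which has a level for permanent damage) or the narrative. That derivation rule should be written down and applied blind to study group.

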### **Outcomes measured among school-age children**

To help interpret results obtained in study children., end of season surveys have also been conducted among school-age children in the study areas at the same time as the end of transmission season surveys. The following outcomes will be calculated for school-age children.

- 3.1. The prevalence of asexual stage *P. falciparum* infection of any density
- 3.2. The prevalence of asexual stage *P. falciparum* infection with a density  $\geq 5000$  per  $\mu\text{l}$

3.3 The arithmetic mean *P. falciparum* parasite density, including samples which are parasite negatives as having a density of zero.

### **Analysis periods and person-years at risk**

Several analysis periods are of interest for the primary outcome of clinical malaria. These are detailed in the figures and text that follow.

Hypothesis testing and p-values will be presented for the whole intervention period (Period A characterised below) and for the two periods of interest in the extension study (periods B and C in the list below). Numbers of events and hazard ratios or other measures of effect (with confidence intervals) will be tabulated for other analysis populations.

#### **A) Whole intervention period (all children).**

The primary analysis population will be the whole intervention period. This is the period starting from enrolment in April 2017 until the end of the intervention year in which children reached 5 years of age (31 March 2021 for *older children*, 31 March 2022 for *younger children*).

#### **B) Study Year 4, to assess effectiveness of the sixth dose of RTS,S/AS01E**

All study children still in follow-up at the start of the fourth year of the study will be included, starting from 1st April 2020 until 31 March 2021 (i.e., covering the 2020 rainy season and subsequent dry season).

#### **C) Study Year 5, to assess effectiveness of the seventh dose of RTS,S/AS01E (younger children only)**

Older children were not eligible for interventions in 2021. Consequently, this analysis will include only younger children, starting from 1st April 2021 until 31 March 2022 (i.e., covering the 2021 rainy season and subsequent dry season).

#### **D) From study start until the end of the study year 4 (to assess the overall effectiveness of up to six doses)**

All children originally enrolled in the trial were scheduled to receive study interventions during the first four years of the trial. This period will be analysed, starting from enrolment in April 2017 until 31 March 2021, after the end of the 2020 rainy season.

#### **E) Whole intervention period, including only *younger children* (those eligible for interventions in 2021)**

Starting from enrolment in April 2017 until 31 March 2022 (i.e. after the end of the 2021 rainy season, in which interventions were given to *younger children* for the last time). This period reflects the 'full' intervention over five years, with up to 7 doses of RTS,S and/or five complete seasons of SMC prior to 5 years of age.

**Figure 3.** Schematic of the analysis periods referred to in the text

Dark blue boxes show the periods that will be included in each analysis. \*Older children are those aged 5 years or above on 1st June 2021, who were not eligible for interventions in Study Year 5 (2021). \$Younger children were aged below 5 years on 1st June 2021, so were eligible for interventions in 2021.

## Analysis strategy

### Modified Intention to Treat

The primary analysis will be by modified intention to treat (mITT). The mITT population will include all children who were screened and who received the first dose of RTS,S/AS01E or control vaccine, irrespective of the number of doses of subsequent vaccines or SMC/SMC placebo received.

Children will contribute time at risk from the date of the first vaccination contact in 2017, until the end of the intervention period, which is either

- i) 31st March 2021, if born prior to 1st June 2016 (and thus over the age of five years in June 2021), or
- ii) 31st March, 2022, if born on or after 1st June 2016, and thus still under the age of five year in June 2021.

Prior to the end of the intervention period, children may be censored;

- 1) on the date last seen if lost-to-follow-up (LT FU),
- 2) on the date of permanent exit from the study area, or
- 3) on the date of death,

Children who temporarily left the study area with known exit and re-entry dates will have the corresponding person-time excluded from the analysis by intention to treat (and per protocol, if leaving the study area does not result in missed treatments).

